CLINICAL STUDY PROTOCOL

Study Title: A Phase 2, Randomized, Active Comparator-Controlled, Open-Label, Adaptive Design Study to Assess the Safety and Efficacy of Intravenously-Administered SelK2 in Patients Undergoing Total Knee Arthroplasty.

Protocol Amendment #1: SELK2-00005, version 2.0 Date: May 21, 2019

Original Protocol: SELK2-00005, version 1.0 Date: September 4, 2018

Drug Name: SelK2: a function-blocking, humanized anti-PSGL-1 monoclonal antibody

Investigational Phase: 2

Prepared by: [name].

[name].

Sponsor: Tetherex Pharmaceuticals Corporation
[name].
Executive Director, Clinical Development
[name]
[name]
[contact]
Email: [contact]

SIGNATURE PAGE

Clinical Study Protocol: **SELK2-00005**

[figure not shown]
Protocol Amendment #1 Date: **May 21, 2019**

Protocol Number: **SELK2-00005, version 2.0**

Study Title: A Phase 2, Randomized, Active Comparator-Controlled, Open-Label, Adaptive Design Study to Assess the Safety and Efficacy of Intravenously-Administered SelK2 in Patients Undergoing Total Knee Arthroplasty.

The undersigned verify that they have read, understood, and concur with this protocol (SELK2-00005) and will comply with all study procedures defined in the protocol.

21 May 2019
Date

[name]. (signature)
Executive Director, Clinical Development
Tetherex Pharmaceuticals, Corp.
Oklahoma City, OK

Date

Principal Investigator (signature)

Principal Investigator (printed name)

PROTOCOL SYNOPSIS

Name of Investigational Product: SelK2: a function-blocking, humanized anti-PSGL-1 monoclonal antibody	
Name of Sponsor Company: Tetherex Pharmaceuticals Corporation	Phase of Development: Phase 2
Title of Study: A Phase 2, Randomized, Active Comparator-Controlled, Open-Label, Adaptive Design Study to Assess the Safety and Efficacy of Intravenously-Administered SelK2 in Patients Undergoing Total Knee Arthroplasty.	
Number of Patients: Approximately 190 patients; with up to 285 patients possible upon activation of the adaptive arm	
Number of Sites: Approximately 25 clinical sites	
Study Population: Male and female patients undergoing elective total knee arthroplasty (TKA)	
Study Duration: Each patient will participate in the study for up to 13 weeks, including an up to 30-day Screening Phase, 11-day Treatment Phase, and a 45-day Follow-up Phase. The end of the trial will occur when the last study visit (Day 57) is completed for the last patient enrolled into this study.	

Study Objectives: The objectives of this study are to:
 
 - Investigate the efficacy of SelK2 as monotherapy in the prevention of VTE (composite of asymptomatic DVT detected by mandatory unilateral venography of the operated leg or confirmed symptomatic DVT, confirmed symptomatic PE or unexplained death) in patients undergoing primary unilateral TKA; - Assess the incidence of bleeding events (major bleeding events, clinically relevant non-major bleeding events, and minor bleeding events) in patients administered SelK2 and undergoing primary unilateral TKA; - Assess the overall safety and tolerability of SelK2 in this patient population; - Further describe the PK and PD of SelK2; - Evaluate the immunogenicity of single dose SelK2; and - To evaluate exploratory efficacy endpoints of inflammation and thrombosis. - Adaptive arm, if activated, assess the efficacy and safety of SelK2 when given in addition to enoxaparin for the prevention of venous thromboembolism (VTE) in patients undergoing primary unilateral TKA. 	

Study Design: This clinical study is a multi-center, randomized, active comparator-controlled, open-label, adaptive design study to assess the safety and efficacy of SelK2 in the prevention of VTE events in patients undergoing TKA. A total of approximately 190 patients planning to undergo unilateral TKA will be recruited into two arms of the study.
 
The two arms of the study will enroll patients in a 1:1 ratio (approximately 95 patients in each arm) as shown below:
 
 1.) 7.5 mg/kg SelK2 (IV, single-dose) 2.) Active Comparator (40 mg Enoxaparin, SC, QD) 
Patients planning to undergo scheduled TKA under general anesthesia who meet all the inclusion criteria and none of the exclusion criteria will be eligible for randomization into this study. Prior to randomization, a Screening Phase consisting of clinical and laboratory evaluations will occur within 30 days prior to randomization to assess patient eligibility for this study. Upon meeting all criteria, patients will be randomized into this study using a centralized randomization system.
	

Following randomization, patients randomized to the SelK2 arm will receive a single dose of 7.5 mg/kg SelK2 via intravenous (IV) administration over a 30-minute time period at least 12 hours but not longer than 24 hours prior to the start of the TKA procedure. Patients randomized to the enoxaparin arm will receive 40 mg enoxaparin administered SC 12 hours after TKA surgery followed by daily injections of 40 mg enoxaparin for at least 9 consecutive days post-surgery and up to the time point of the venography (with the option of giving an additional 40 mg enoxaparin, SC dose 12 hours prior to TKA surgery).

For all patients, the TKA procedure will be done on Study Day 2. Patients will be required to spend at least 2 nights after TKA procedure in the hospital, and patients, at the discretion of the PI, can remain in the hospital at least up to the day of the venography.

All patients will be required to undergo unilateral ascending venography of the operated leg 10 ± 2 days post-surgery (Study Day 11 ± 2 days). After completion of the venogram, patients will be released from the clinical setting, and this will conclude the Treatment Phase of the study.

The Follow-up Phase of this study will consist of two clinic visits on Days 21 and 57 and two follow-up telephone contacts on Days 29 and 43. The final study visit occurs on Day 57 (Day 57/Early Discontinuation Visit).

Data on all asymptomatic deep vein thrombosis (DVT) as determined by venogram and symptomatic clinical VTE will be collected during both Treatment and Follow-up Phases of the study. Bleeding events and other safety and clinical laboratory assessments including exploratory markers of inflammation and thrombosis, coagulation parameters and bleeding events will be performed throughout both the Treatment and Follow-up Phases. Data on all suspected arterial thrombotic events will also be collected. Blood samples will be collected for PK, PD, and immunogenicity analyses.

A Central Independent Adjudication Committee (CIAC) will assess all venograms, symptomatic VTE outcomes (including DVT and PE), bleeding events, suspected stroke, any other suspected arterial thrombotic events, and death. Adjudicators will be blinded to treatment assignment.

A Steering and Safety Committee will conduct ongoing reviews of all safety and efficacy data in an unblinded fashion.

Adaptive Design: The Steering and Safety Committee and Sponsor will review the accumulating efficacy and safety data at planned intervals, and based upon the safety and efficacy profile of SelK2 may decide to modify enrollment by adding a third study arm testing 7.5 mg/kg SelK2 given in addition to enoxaparin (40 mg, SC, QD) and removal of the SelK2 only arm. The two remaining arms will enroll patients in a 2:1 ratio with two patients receiving SelK2 and Enoxaparin for every one patient receiving Enoxaparin only at doses shown below:

- 1.) 7.5 mg/kg SelK2 (IV, single-dose) and 40 mg Enoxaparin, SC, QD
- 2.) Active Comparator (40 mg Enoxaparin, SC, QD)

Criteria for Selection of Patients:*Inclusion Criteria:*

1. Males or females, between 18 and 80 years of age, inclusive;
2. Females must be non-pregnant and non-lactating, and either postmenopausal (>12 months since last menses) or using highly effective contraceptive measures as defined by the Clinical Trial Facilitation Group (CTFG) guidelines;
3. Males, if engaged in sexual relations with a partner of child-bearing potential, must use highly effective contraceptive measures as defined by the Clinical Trial Facilitation Group (CTFG) guidelines;
4. Planned to undergo elective, primary total unilateral TKA under general anesthesia; and
5. Able to comprehend and willing to give written informed consent.

Exclusion Criteria:

Patients presenting with any of the following will not be included in the study:

1. Body weight <50 kg at Screening;
2. Previous deep vein thrombosis (DVT) of the leg or pulmonary embolism (PE) within the past year;
3. Malignancy within 1 year, except for basal or squamous cell carcinoma of the skin or carcinoma *in situ* of the cervix that has been successfully treated;
4. Myocardial infarction, transient ischemic attack or stroke within the last 6 months;
5. Patients at increased risk of bleeding because of history of increased bleeding tendency (i.e., history of bleeding diathesis) or any other condition that in the opinion of the Investigator increases risk of bleeding (e.g., recurrent gastrointestinal ulcer) or patients with a history of intracranial or intraocular bleeding;
6. Brain, spinal, or ophthalmologic surgery within the past 3 months;
7. Cockcroft-Gault calculated creatinine clearance <30 mL/min at Screening (central lab will calculate the Cockcroft-Gault value);
8. Screening laboratory results as follows, or any other clinically significant abnormalities in screening laboratory values that, in the opinion of the PI, would render a patient unsuitable for inclusion:
 - ALT or AST >1.5x ULN
 - Total bilirubin >1.5x ULN
 - Platelet count <150,000 or recent (over the last 3 months) history of thrombocytopenia (e.g. platelet count <150,000);
9. Positive test for human immunodeficiency virus (HIV; by history of having HIV antibodies), positive hepatitis B (hepatitis B surface antigen [HBsAg]) or hepatitis C (anti-hepatitis C antibody [Anti-HCV]) at Screening;
10. Uncontrolled hypertension as judged by the Investigator;
11. Clinically significant abnormal ECG at Screening, as judged by the Investigator;
12. Active infection;
13. Unable to undergo venography due to a known allergy to the contrast agent, anticipated poor venous access, impaired renal function, or any other reason identified and specified by the PI;
14. Hypersensitivity to enoxaparin or any contraindication listed in the local labeling of enoxaparin;
15. Any underlying condition (e.g., atrial fibrillation, mechanical heart valve, or recent pulmonary embolism) that may lead to the required concomitant use of anticoagulants/antiplatelet agents (e.g., warfarin, dabigatran, rivaroxaban, apixaban, clopidogrel) that may affect study outcome or any other drug influencing coagulation (except low dose aspirin (100 mg or less));
16. Anticipated use of intermittent pneumatic compression devices and/or electrical/mechanical muscle stimulators post TKA procedure;

17. Anticipated use of indwelling intrathecal or epidural catheters;
18. Participation in any other investigational study drug trial in which receipt of an investigational study drug occurred within 60 days prior to Day 1;
19. History of alcoholism or drug addiction within 1 year prior to Screening;
20. Any acute or chronic condition that, in the opinion of the Investigator, would limit the patient's ability to complete and/or participate in this clinical study; or
21. Unwillingness to comply with all study procedures including follow-up visits, as specified by this protocol, or unwillingness to cooperate fully with the Investigator.

Duration of Treatment:

During the Treatment Phase of this study each patient will receive either:

- 1) A single 7.5 mg/kg dose of SelK2 administered intravenously 12 to 24 hours prior to the initiation of the TKA surgery, or
- 2) 40 mg dose of enoxaparin (active comparator) administered SC 12 hours after TKA surgery followed by daily injections of 40 mg enoxaparin, SC for at least 9 additional days post-surgery and up to the day of the planned venography (with the option of giving an additional 40 mg enoxaparin, SC dose 12 hours prior to TKA surgery).

Upon activation of the adaptive arm and discontinuation of the SelK2 only arm of the study, during the Treatment Phase each patient will receive either:

- 1) A single 7.5 mg/kg dose of SelK2 administered intravenously 12 to 24 hours prior to the initiation of the TKA surgery AND 40 mg dose of enoxaparin administered SC 12 hours after TKA surgery followed by daily injections of 40 mg enoxaparin, SC for at least 9 additional days post-surgery and up to the day of the planned venography, or
- 2) 40 mg dose of enoxaparin (active comparator) administered SC 12 hours after TKA surgery followed by daily injections of 40 mg enoxaparin, SC for at least 9 additional days post-surgery and up to the day of the planned venography (with the option of giving an additional 40 mg enoxaparin, SC dose 12 hours prior to TKA surgery).

Each randomized patient will undergo TKA surgery on the Day 2 of the study. Patients must stay hospital for at least 2 nights after the TKA. A mandatory venogram will be completed on Study Day 11 (\pm 2 days). Completion of venography will conclude the Treatment Phase of the study. Patients will then enter a Follow-up Phase of the study which will consist of two clinic visits on Days 21 and 57 and follow-up telephone contacts on Days 29 and 43. The final study visit occurs on Day 57 with a complete set of laboratory and safety assessments. Prior to enrollment into the study, a Screening Phase consisting of clinical and laboratory evaluations will occur within 30 days prior to randomization to assess patient's eligibility for this study. Each patient will participate in the study for up to approximately 13 weeks, including an up to 30-day Screening Phase, 11-day Treatment Phase, and a 45-day Follow-up Phase.

Test Product, Dose Preparation, and Mode of Administration:**Study Drug (SelK2):** [REDACTED]

[REDACTED] Vials are stored refrigerated at 2 to 8°C and protected from light. A pharmacist or designated personnel will compound individual doses of active study drug for patients on a milligram per kilogram basis in a 100 mL infusion bottle or bag of a sterile 0.9% sodium chloride solution (0.9% Sodium Chloride Injection, USP) in accordance with the Pharmacy Manual. Study drug will be administered over 30 minutes by IV infusion.

Active Comparator (Enoxaparin): Commercially available enoxaparin (40 mg in 0.4 mL water

in pre-filled disposable syringes for SC administration) will be provided to the study site pharmacies for use in this study, in accordance with local regulatory requirements. Enoxaparin should be stored in a temperature-controlled environment which is maintained below 25°C; but should not be frozen.

The Pharmacy Manual will provide further details about handling, storage, and mode of administration.

Dose Rationale:

Criteria for Evaluation:

Primary Efficacy Endpoints: The primary efficacy outcome is the composite of asymptomatic deep vein thrombosis (DVT) detected by mandatory unilateral venography of the operated leg or confirmed symptomatic DVT, confirmed symptomatic PE or unexplained death during the Treatment Phase. All efficacy endpoint data will be adjudicated by a blinded Central Independent Adjudication Committee.

Exploratory Efficacy Endpoints: The exploratory efficacy outcomes will include measurements of markers of inflammation and thrombosis (hsCRP and D-dimer, respectively) and other possible PD markers of SelK2 efficacy.

PK, PD, and Immunogenicity Evaluations: Samples will be collected during Treatment and Follow-up Phases for evaluation of PK, PD, and immunogenicity.

Safety:

The primary safety outcome is a composite of major bleeding events or clinically relevant non-major bleeding events during the Treatment Phase. The secondary safety outcomes are the incidence of the composite of major, clinically relevant non-major, or minor bleeding events that occur during the Treatment and Follow-up Phases.

Other safety evaluations will include assessment of adverse events, physical examinations, 12-lead ECGs, vital signs (including temperature, respiratory rate, and seated blood pressure and pulse), clinical chemistry laboratory evaluations, additional laboratory evaluations including prothrombin time/international normalized ratio (PT/INR), activated partial thromboplastin time (aPTT), hematology panel, urinalysis, and pregnancy test (female patients of child bearing potential only).

Statistical Methods:

Demographic and other patient data will be summarized by treatment group using descriptive statistics.

The primary efficacy comparison will compare the SelK2 only-treated, SelK2 and enoxaparin-treated, and enoxaparin only-treated arms. The difference in the total VTE rate determined during the entire Treatment Phase will be estimated. The 1-sided lower 90% CI of the difference between the SelK2 and enoxaparin groups only arms as well as the difference between the adaptive arm (SelK2 and enoxaparin) and enoxaparin only arms will be calculated and non-inferiority will be concluded if the upper limit of the 90% CI is $\leq 15\%$. Absolute changes from baseline in levels of high-sensitivity CRP and D-dimer will be assessed. A number of secondary analyses may be conducted to assess the robustness of the primary analysis finding.

SelK2 concentrations will be summarized by descriptive statistics.

Safety will be assessed by reported adverse events, changes from baseline during treatment in vital signs, ECGs, laboratory parameters, and physical examination and will be summarized using descriptive statistics. Adverse events will be coded using the (Medical Dictionary for Regulatory Activities) MedDRA dictionary and summarized by system organ class, preferred term, Investigator causality assessment, and treatment group. Incidence of bleeding events (as adjudicated by CIAC) will be tabulated by treatment group.

Sample Size Considerations:

Assuming that the rate of VTE for the active comparator (enoxaparin) arm of this study will be 25%, it is estimated that a sample size of 76 evaluable patients per arm should give the study 80% power of declaring non-inferiority between the SelK2 only arm and the enoxaparin active comparator arm. This calculation uses a one-sided 90% CI with a non-inferiority margin of 15%. This calculation assumes that the underlying rate of VTE for the SelK2 and enoxaparin arms will be identical at 25% and with the non-inferiority margin set as the midpoint between the expected active therapy response compared with an assumed placebo event rate in this patient population of 55%. Consequently, making the conservative estimate that up to 20% of randomized patients may not have evaluable endpoint data; a total of 95 patients will be enrolled per arm to provide at least 76 endpoint evaluable patients per arm.

Sample Size Considerations for Adaptive Arm:

With the same assumptions as above for the active comparator (enoxaparin) arm of the study event rate, it is estimated that a sample size of 76 evaluable patients in a combination therapy arm of SelK2 and enoxaparin should give the study 80% power of declaring superiority between the SelK2 and enoxaparin and the enoxaparin active comparator arm for an estimated SelK2 and enoxaparin VTE event rate of 6% (a 19% difference between combination treatment effect and active comparator treatment effect). This calculation assumed a two-sided 0.1 alpha, a Pearson Chi-squared test, and a superiority comparison.

TABLE OF CONTENTS

PROTOCOL SYNOPSIS	iii
1.0 INTRODUCTION	1
1.1 Background	1
1.2 Preclinical Studies Supporting SelK2 Antithrombotic Activity	2
1.2.1 In Vivo Mechanism of Action	2
1.2.2 Toxicology	2
1.2.3 Absorption, Distribution, Metabolism, and Excretion	3
1.3 Clinical Studies of SelK2.....	4
1.4 Study Rationale	7
1.5 Rationale for the Dose Regimen	7
2.0 STUDY OBJECTIVES	8
3.0 STUDY DESIGN	9
3.1 Basic Design Characteristics.....	9
3.2 Number of Patients.....	9
3.3 Study Population	10
3.4 Study Phases.....	10
3.4.1 Screening Phase	10
3.4.2 Treatment Phase.....	10
3.4.3 Follow-Up Phase	11
3.4.4 Study Diagrams for SelK2 and Enoxaparin Arms	11
3.5 Efficacy and Safety Assessments.....	12
3.6 Endpoints	13
3.6.1 Primary Efficacy Endpoint.....	13
3.6.2 Exploratory Efficacy Endpoints	13
3.6.3 Pharmacokinetic Assessments of SelK2	13
3.6.4 Pharmacodynamic Assessments of SelK2	14
3.6.5 Safety Endpoints	14

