10.0 STATISTICAL METHODS AND PLANNED ANALYSES

10.1 Sample Size and Power

Assuming that the rate of VTE for the active comparator (enoxaparin) arm of this study will be 25%, it is estimated that a sample size of 76 evaluable patients per arm should give the study 80% power of declaring non-inferiority between the SelK2 arm and the enoxaparin active comparator arm. This calculation uses a one-sided 90% CI with a non-inferiority margin of 15%. This calculation assumes that the underlying rate of VTE for the SelK2 and enoxaparin arms will be identical at 25% and with the non-inferiority margin set as at the midpoint between the expected active therapy response compared to an assumed placebo event rate in this patient population of 55%. Consequently, making the conservative estimate that up to 20% of randomized patients may not yield evaluable endpoint data, a total of 95 patients will be enrolled per arm to provide at least 76 endpoint evaluable patients per arm.

Sample Size Considerations for Adaptive Arm:

With the same assumptions as above the for active comparator (enoxaparin) arm of the study event rate, it is estimated that a sample size of 76 evaluable patients in a combination therapy arm of SelK2 and enoxaparin should give the study 80% power of declaring superiority between the SelK2 and enoxaparin arm and the enoxaparin active comparator arm for an estimated SelK2 and enoxaparin VTE event rate of 6% (an 19% difference between combination treatment effect and active comparator treatment effect). This calculation assumes a two-sided 0.1 alpha, a Pearson Chi-squared test, and a superiority comparison.

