10.3 Statistical Analysis

10.3.1 General Considerations

Descriptive summary statistics include mean, median, standard deviation, interquartile range, and range (minimum, maximum) for continuous variables, and counts and percentages for categorical

variables. Unless otherwise specified, continuous variables will be analyzed using two-sample t-test or Wilcoxon-Mann-Whitney test, whichever is appropriate; and categorical variables will be analyzed using chi-squared test or Fisher's exact test, whichever is appropriate.

SAS 9.3 or later will be used to perform statistical analysis. Unless otherwise specified, a two-sided p-value less than 0.05 will be considered statistically significant. No multiplicity adjustment will be made.

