10.3.3 Efficacy Analyses

For all efficacy analyses, the main analysis will be based on the mITT population. Both primary and secondary endpoint analyses will also be performed on the PP population; these analyses will be supportive only. Comparisons will be made between the SelK2 treated patients SelK2 and enoxaparin treated patients, and the enoxaparin group. The difference of the total VTE rate during the Treatment Phase (from time of randomization up until the day of completion of venogram) between the SelK2, SelK2 and enoxaparin, and enoxaparin treatment groups will be estimated. The lower 1-sided 90% CI of the difference will be calculated and non-inferiority will be concluded if the upper limit of the 90% CI is $\leq 15\%$. The same analysis will be completed on the PP population.

The following secondary analyses will be performed on the mITT and PP populations:

- Comparison of the rates of the individual components of the primary efficacy outcome between the SelK2, SelK2 and enoxaparin, and enoxaparin treatment groups through Treatment Period.
- Conduct primary efficacy analysis of the total VTE rate between the SelK2 treatment, SelK2 and enoxaparin treatment, and enoxaparin treatment with the inclusion of events through Study Day 57.
- Complete comparison of the rates of the individual components of the primary efficacy outcome between the SelK2, SelK2 and enoxaparin, and enoxaparin treatment groups with the inclusion of events through Study Day 57.

Absolute changes from baseline in hsCRP and D-dimer will be summarized by treatment group at each post-baseline visit. Change from baseline in each parameter will be analyzed and compared between treatment groups using a mixed linear model with repeated measures (MMRM).

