10.5 Steering and Safety Committee Data Reviews and Interim Analyses

A formal study Steering and Safety Committee will consist of at least 3 clinicians (with experience and expertise in venous thrombosis). The Steering and Safety Committee will be charged with reviewing in an unblinded fashion all accumulating safety and efficacy data to assure overall patient safety in this study.

The following efficacy and safety data will be provided to the Steering and Safety Committee by treatment group, and where appropriate by study visit day and time:

- Overall VTE event rate (as adjudicated);
- Individual component event rate (individual components of the composite VTE event rate);
- Incidence of bleeding events (as adjudicated) including the following will be tabulated by treatment:
 - 1) Major Bleeding event (MB),
 - 2) Clinically Relevant Non-Major Bleeding event (CRNMB),
 - 3) Minor Bleeding even, or
 - 4) Combination of MB and CRNMB
- Incidence of AEs (including SAEs) ;
- Clinical laboratory values (hematology, serum chemistries, urinalysis, and coagulation parameters);
- ECGs; and
- Vital signs.

The Steering and Safety Committee will use all of the above accumulating data to assess the safety of continuing each aspect of this study.

Interim Analyses to support decision on whether or not to recommend activation of Adaptive Arm:

The Steering and Safety Committee is also charged with making recommendations to the Sponsor with regards to the activation of the adaptive arm that investigates the efficacy and safety of SelK2 use in combination with enoxaparin. At certain enrollment milestones, the Steering and Safety Committee will be presented with interim analysis tables which will include VTE event rates by treatment group with 80% confidence intervals and the calculated risk difference (the difference

between the cumulative incidence in the SelK2 arm to that of the cumulative incidence the enoxaparin arm) with 80% confidence intervals. The conditional powers for demonstrating non-inferiority at the end of the trial based upon accumulated data at interim may also be computed. These interim analyses will be part of the data set used by the Committee as they determine whether or not to recommend activation of adaptive arm. This adaptive arm may be initiated if the Steering and Safety Committee determines that preliminary data suggests the potential for an additive effect in VTE reduction and that the combination does not pose an additional safety risk.

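### Closing the SelK2-only arm on its own interim VTE results and then applying the unadjusted 90% limit means the one-sided 10% error rate is not held and can be exceeded

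*Combined protocol and SAP*

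**What the plan says.** - **Decision and its basis.** Under Adaptive Design, the synopsis has the committee and sponsor look at accumulating data at planned intervals. It says that they, "based upon the safety and efficacy profile of SelK2 may decide to modify enrollment by adding a third study arm", and the same sentence removes the SelK2-only arm. Section 5.1.3 also treats activation and closure as one step, after which allocation is 2:1 combination to enoxaparin.
- **Trigger.** Sections 1.4 and 10.5 give one criterion. The committee must judge that "preliminary data suggests the potential for an additive effect in VTE reduction" exists and that the combination adds no safety risk. No number is attached.
- **What is seen.** Under Section 10.5 the committee sees, unblinded and at unspecified enrolment milestones, VTE rates by arm and their difference with 80% intervals. Conditional power for non-inferiority is optional.
- **Final rule.** The synopsis and Section 10.3.3 keep SelK2-only against enoxaparin in the primary comparison, and "non-inferiority will be concluded if the upper limit of the 90% CI is" at or below 15%. Section 10.3.1 adds: "No multiplicity adjustment will be made".
- **Sizing.** Section 10.1 states that "a sample size of 76 evaluable patients per arm should give the study 80% power of declaring non-inferiority", with a one-sided 90% interval and 25% VTE in both arms.

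**The concern.** No patient receives the combination before activation, so the in-trial efficacy evidence for activating must come from SelK2-only against enoxaparin. The final size of the SelK2-only arm can therefore depend on that arm's own results, and the one stated reason for closing it is a favourable one. If the interim 80% interval is two-sided, its upper limit is the same one-sided 90% limit used in the final decision, so the deciding statistic is on view at every look.

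A fixed-sample limit applied after such a closure does not keep its nominal level. At stake are the error rate behind the primary monotherapy conclusion and an estimate that can be shifted toward SelK2. This is separate from the power lost by stopping the arm short.

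**Working it through.** **1. Reproduce the plan's figure.** Inputs from Section 10.1: 25% in both arms, margin 0.15, one-sided level 0.10 (z = 1.2816), power 80% (z = 0.8416).

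n = (1.2816 + 0.8416)² × 2 × 0.25 × 0.75 / 0.15² = 75.1, so 76 per arm; 76 / 0.80 = 95 enrolled. Power at 76 is Φ(0.15/√(0.375/76) − 1.2816) = Φ(2.135 − 1.282) = 80.3%. A one-sided 0.05 level would need 104 per arm, so 10% is the design error rate.

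**2. Set the null.** With enoxaparin at 25% and a 15-point margin, the boundary is SelK2 at 40%.

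**3. Simulate closure** (1,000,000 trials per setting; simulation error about 0.1 point). Assumed, because the plan gives none of it: looks at 38 evaluable per arm, or at 25 and 38; the closing rules in the table; an unpooled Wald limit. At the first look that meets the rule, SelK2-only closes and the unadjusted 90% limit is applied. Controls are either all enoxaparin patients (76) or only those enrolled concurrently with SelK2-only.

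| Assumed closing rule | Looks | All enoxaparin | Concurrent |
|---|---|---|---|
| Never | none | 9.9% | 9.9% |
| SelK2 rate at or below enoxaparin | 38 | 12.0% | 15.1% |
| | 25, 38 | 13.8% | 16.5% |
| Limit already at or below 15 points | 38 | 12.2% | 15.3% |
| | 25, 38 | 13.8% | 18.9% |
| Difference at most 10 points | 38 | 12.1% | 12.0% |
| | 25, 38 | 13.3% | 11.9% |
| Difference below 30 points | 38 | 10.9% | 10.2% |
| | 25, 38 | 11.6% | 10.1% |
| Below 30 points, limit not yet passed | 38 | 8.6% | 4.8% |
| | 25, 38 | 8.6% | 3.0% |

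The 30-point value is the assumed 55% placebo rate minus 25%. If the arm closes at 25 and 76 combination patients follow at 2:1, enoxaparin ends at 25 + 38 = 63 and not 76; with that count the two-look figures for the first two closing rules are 14.0%.

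Further rules: closing at a difference of 0 or less, or of 15 points or more, gives 11.5-15.0%. Closing only for unfavourable results gives 7.8-9.4%.

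**4. Shift in the estimate.** At the null, the mean estimated difference without closure is 15.0 points. Under the first two closing rules it is 12.6 to 14.5, a shift of 0.5 to 2.4 points toward SelK2. Looser favourable triggers shift it by up to about 4 points.

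**5. What an early-closed arm could have shown.** Fixed-size power with the 90% limit, concurrent controls, 25% in both arms:
- 25 per arm: Φ(0.15/√(0.375/25) − 1.282) = Φ(1.225 − 1.282) = 48%.
- 38 per arm: Φ(0.15/√(0.375/38) − 1.282) = Φ(1.510 − 1.282) = 59%.

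**The case against.** The strongest objection concerns direction. The synopsis refers to the profile of SelK2 without saying good or bad, and the additive-effect wording is attached to starting the combination. Additive does not mean as good as enoxaparin: a drug with 40% VTE against an assumed placebo rate of 55% could look additive and still be worse than enoxaparin. Replacing monotherapy with an add-on arm fits a reading of active but not sufficient, and under that rule the error drops to 3.0-8.6%. This stands. A reader might infer that false non-inferiority does exceed 10%; the documents do not support that, because they fix no rule.

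The control set also matters. Enoxaparin keeps enrolling after closure, Section 10.3.3 refers to a single enoxaparin group, and nothing restricts the test to concurrent patients. The figures of 15-19% need that unstated restriction; the more natural reading gives 11-14%. This stands too.

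Other points carry less weight. Look times may be in the committee charter, which is not available here, but the decision limit is stated in Section 10.3.3 and a charter schedule would not change it. The multiplicity sentence follows the general 0.05 rule and does not mention interim looks, yet no other adjustment appears. A phase 2 trial can tolerate a 10% error rate, but the design already uses that tolerance, and Section 1.4 intends the data to support a claim of efficacy.

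**Conclusion.** The concern holds in this form: the SelK2-only arm may be closed on its own unblinded interim results, with a favourable signal as the only stated trigger, and the fixed-sample limit then applied does not hold the 10% error rate behind the sizing. Under the favourable triggers in the table the rate is about 11-14% with all enoxaparin patients and about 10-19% with concurrent controls, against 9.9% with no closure. It falls below 10% under unfavourable-only closure and under the rule of active but not yet meeting the margin. All of these sizes rest on assumed looks, triggers and control sets, and on rates of 25% and 40%. The firm conclusion is that the plan cannot state the error rate of its primary monotherapy test once the arm closes early, and that the rate can exceed 10%.

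**What to change.** Add to Sections 10.3.3 and 10.5: if the SelK2-only arm closes before its planned size, its difference from enoxaparin is reported with a confidence interval as estimation only, and no non-inferiority conclusion is drawn. The 15-point rule applies only if the arm reaches its planned size. Name the enoxaparin control set (all patients or concurrent only).

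The cost is SAP wording, with nothing lost if the arm completes. An early-closed arm gives up a conclusion that, as a fixed-size test at one third to one half of 76 per arm, would have had about 48-59% power. Among arms closed because they looked good the pass rate would be higher, but that selection is what makes the conclusion unreliable.

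If the sponsor wants to keep a conclusion after early closure, it should use a group-sequential limit computed for the actual look times and control set. As an illustration, O'Brien-Fleming-type spending at one third, one half and full information gives z = 2.62, 2.08 and 1.318. Power is Φ(2.135 − 1.318) = 79.3% at the full 76, but that figure does not describe an arm closed early. There it is about Φ(1.510 − 2.08) = 28% at one half and Φ(1.225 − 2.62) = 8% at one third. These limits also do not carry over to all 76 enoxaparin patients: with 38 SelK2 patients the information fraction is (2/76)/(1/38 + 1/76) = 2/3, not 1/2. The plan should say that power after early closure is much lower.
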